5.2.5 Post-operative Follow-up/End of Surgical Treatment Visit (EOT)

These include one follow-up at week 1, one month, three months (EOT), six months, nine months, 12 months, 15 months, 18 months, 21 months, and 24 months after radical surgery, whichever occurs first, until the patient develops disease progression, dies, withdraws informed consent, loses follow-up, concludes the study follow-up, or begins new anticancer therapy (surgery).

End-of-surgical visit (EOT) was performed 90 days postoperatively (-14 to+28 days).

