5.3.4 Tumor and Efficacy Evaluation

5.3.4.1 baseline neoplastic imaging will be performed prior to enrollment with multiparameter magnetic resonance imaging of the bladder (or pelvis) (which must be reassessed post-TURBT if TURBT) and computed tomography (CT) scans of the chest, whole abdomen, and pelvis (enhancement to be determined by the investigator if necessary).

While 5.3.4.2 is on treatment, multiparameter magnetic resonance imaging of the bladder (or pelvis) will be performed (with a conditional VI-RADS score) and computed tomography (CT) scans of the chest, whole abdomen, and pelvis (enhancement at the discretion of the investigator if

necessary) prior to and prior to the start of cycle 3 of neoadjuvant therapy according to RECIST version 1.1:

1. Assessed prior to the start of cycle 3 and continued treatment as planned if the patient did not develop PD; • if the patient has PD, subsequent treatment at the discretion of the investigator;

2. Pre-operative evaluation. If the patient meets the operation indication, the researcher shall select appropriate time to perform radical cystectomy according to the plan; If the patient is not suitable for surgery, the investigator decides to give subsequent treatment;

3. After radical surgery, the pathological stages after neoadjuvant treatment will be evaluated by the researchers based on the pathological results of surgical samples.

4. Computed tomography (CT) scans of the chest, whole abdomen, and pelvis are performed 3 months, 6 months, 12 months, 18 months, and 24 months after the radical resection (enhancement is judged by the researcher if necessary). The former shall prevail until the disease progression, death, withdrawal of informed consent, loss of follow-up, conclusion of study follow-up or initiation of new anti-cancer treatment (surgery) of the patient occur.

The investigator will evaluate the response using RECIST 1.1.

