5.3.5 Visit window

All visits during neoadjuvant therapy were to be within the range of -3 to +7 days of the planned date, and postoperative visits were considered to be 14 days, unless otherwise noted. Evaluations scheduled for the day of study treatment dosing (Day 1) per cycle should be completed prior to study treatment infusion/dosing, unless otherwise noted. Laboratory and imaging results should be reviewed prior to dosing. Scheduling a study visit at a protocol-specified time point that is in conflict with a holiday, weekend, or other event/law will allow the visit to be scheduled to the nearest feasible date.

Visit schedule

	sift	Treatment period (one cycle every 21 days)				Drug safety follow-up r	operation		Postoperative follow-up				
		Cycle 1	Cycle 2	Cycle 3	Cycle 4		Preoperative evaluation	Radical resection	1 week	1 month	3 months (EOT)	6, 12, 18, 24 months	9, 15, 21 months
fate (window)	-28 to -1	one	-3 to +7	-3 to +7	-3 to +7	28 after last dose (-3 to +7)	-7 to 0	28 – 42 after the last dose	±3	±7	±14	±14	±14
Informed consent a	X												
Demographic data/ Treatment historyb	X												
Physical examination/vital signs c	X	X	X	X	X	X	X		X	X	X	X	
ECOG assessment	X	X	X	X	X	X	X		X	X	X	X	
Surgical fitness evaluation	X						X						
Electrocardiogram d	X	X	X	X	X	X	X		X	X	X		
Hematology e	X	X	X	X	X	X	X		X	X	X	X	
Serum biochemistry e	X	X	X	X	X	X	X		X	X	X	X	
Urinalysis e	X	X	X	X	X	X	X		X	X	X	X	
Fecal analysise	X			X			X						

Coagulation e	X						X						
Pregnancy testf	X					X	X						
Hepatitis b two half qualitative g	X						X						
Hepatitis c qualitative g	X						X						
Venereal disease (HIV)g	X						X						
Marker screening (HER2 IHC)	X												
Thyroid functionh	X						X						
Chest CT plain scan i	X			X		X	X				X	X	
Total abdominal+pelvic CT plain scan+enhanced i	X			X		X	X				X	X	
Bladder (or pelvis) Multiparameter mri	X			X			X						
Bone scan i	X												
Previous/concomitant medications	X	X	X	X	X	X	X	X	X	X			
Adverse eventj	X	X	X	X	X	X	X	X	X	X	X		
Vidicon monoclonal antibody administration k		X	X	X	X								
Ampley monoclonal antibody administration l		X	X	X	X								
Radical resection and pathological evaluation m								X					
Archived/fresh tumor histon	X							X					
EQ-5D-5L/ EORTC QLQ-C30 o	X	X	X	X	X	X	X	X	X	X	X	X	
Living condition	X	X	X	X	X	X	X	X	X	X	X	X	X

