5.4.3 Efficacy analysis

Analysis of primary effectiveness endpoint for 5.4.3.1

The primary endpoint, the pathological complete response rate (pCR rate), was defined as the proportion of patients in the efficacy analysis set who received radical cystectomy after completion of neoadjuvant therapy without residual tumor lesions as assessed by the investigator. Will be analyzed based on the validity analysis set.

5.4.3.2 secondary efficacy endpoint analysis

The pathological descending rate is determined according to the pathological results after surgery to determine whether the disease is descending to below T2. The percentages of CT2N0 → PT0N0, CT3-4AN0 → PT0N0, CT2N0 → \leq PT 1N0, CT3-4AN0 → \leq PT 1N0 were calculated respectively, and the 95% confidence interval (CI) of bilateral Clopper-Pearson for pathological stage reduction rate was calculated, to evaluate the accuracy of the estimate of pathological stage reduction rate. Will be analyzed based on the validity analysis set.

Event-free survival (EFS), is the time from the first neoadjuvant treatment until disease progression, death from any cause, or new onset of other tumors. The Kaplan-Meier(KM) method

will be used to estimate the no-event curve and the corresponding quantiles (including median values). If the two-sided 95% confidence interval for the median can be estimated, the generalized Brookmeyer and Crowley method (Brookmeyer and Crowley, 1982) was used. The KM method will be used to estimate EFS rates at 1 and 2 years from the first dose, and 1 and 2 years after surgery, with the corresponding 95% confidence interval estimated using Greenwood's formula (Greenwood, 1926). The EFS deletion criteria will be in compliance with the FDA Industry Guide: Clinical Trial Endpoints for Approval of Cancer Drugs and Biological Products (FDA 2007). EFS will be analyzed based on the security analysis set.

Overall survival (OS) was defined as the time from the start of treatment to death for any cause. OS will perform similar analyses using the KM method above for populations included in the safety and efficacy analysis sets, respectively. The time curve will be plotted against the KM estimate of OS. The median OS, OS rates 1 and 2 years from the first dose, and OS rates 1 and 2 years after surgery will be calculated and show a bilateral 95% CI.

5.4.4 safety analysis

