7.2 Provisions for Conclusion of Clinical Trials

The trial ended when all subjects:

1) All subjects complete a survival follow-up of at least 2 years;

2) or all subjects died, were lost to follow-up, or withdrew their informed consent.

VIII. Adverse events and unexpected events

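### Section 5.2.5 stops every post-operative visit, including those that record only survival status, at progression or new therapy, whereas 7.2 requires two years of survival follow-up for all subjects

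*Protocol*

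**What the plan says.** - **Visit rule (5.2.5).** Visits fall at week 1 and at months 1, 3, 6, 9, 12, 15, 18, 21 and 24 after radical surgery. One stop list governs them all, with the earliest event deciding: they run "until the patient develops disease progression, dies, withdraws informed consent, loses follow-up, concludes the study follow-up, or begins new anticancer therapy (surgery").
- **Visit schedule (5.3.5).** The row "Living condition" is marked in all 13 columns. The next fullest row, the quality-of-life questionnaires, has 12 marks and is blank for months 9, 15 and 21.
- **End of trial (7.2).** The trial ends when "All subjects complete a survival follow-up of at least 2 years", "or all subjects died, were lost to follow-up, or withdrew their informed consent". Neither progression nor new therapy is an exit.
- **OS analysis (5.4.3.2).** OS runs from start of treatment to death from any cause. "OS will perform similar analyses using the KM method above for populations included in the safety and efficacy analysis sets, respectively". The outputs are "The median OS, OS rates 1 and 2 years from the first dose, and OS rates 1 and 2 years after surgery".
- **Imaging (5.3.4).** Post-operative CT is "performed 3 months, 6 months, 12 months, 18 months, and 24 months after the radical resection", with its own stop list naming the same events as 5.2.5.

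**The concern.** 5.2.5 and 7.2 give a site different instructions for an operated patient who progresses and is still alive. Under 5.2.5 the visits end, and with them the only scheduled survival contacts. Under 7.2 that patient still owes survival follow-up up to two years.

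OS is what is at stake. Kaplan-Meier treats a censored patient as having the same future risk of death as those still followed. A patient censored because of progression will usually have a higher risk, so stopping at that point would make the estimated curve too high. The SAP can define how such patients are censored, but it cannot recover survival status that was never collected. The visit rule is therefore a matter for the protocol.

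**Working it through.** **1. Can 5.2.5 be read as stopping only imaging or clinic assessments?** Two facts in the protocol work against this.

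- The imaging stop is already written separately in 5.3.4, so the list in 5.2.5 governs the visits themselves.
- Months 9, 15 and 21 are named in 5.2.5, and the schedule marks only survival status there. At those visits the stop rule has nothing else to act on.

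**2. 5.2.5 against 7.2, for an operated patient.**

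| Event | Ends visits under 5.2.5 | Excuses two-year survival follow-up under 7.2 |
|---|---|---|
| Death | yes | yes |
| Loss to follow-up | yes | yes |
| Consent withdrawn | yes | yes |
| Disease progression | yes | no |
| New anticancer therapy | yes | no |

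The two sections disagree on the last two rows.

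**3. Visits removed.** The ten visits are week 1 and months 1, 3, 6, 9, 12, 15, 18, 21 and 24. Progression is taken as found at a scheduled CT.

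| CT showing progression | Visits dropped | Of these, survival status only | Months to 2 years after surgery without a scheduled contact |
|---|---|---|---|
| Month 3 | 7 | 3 (9, 15, 21) | 24 − 3 = 21 |
| Month 6 | 6 | 3 (9, 15, 21) | 24 − 6 = 18 |
| Month 12 | 4 | 2 (15, 21) | 24 − 12 = 12 |
| Month 18 | 2 | 1 (21) | 24 − 18 = 6 |

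**4. The same gap to the 2-year landmark from first dose.** Assumptions: four 21-day cycles, first dose on day 1, a month of 30.44 days.

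- Fourth dose: day 1 + 3 × 21 = day 64.
- Surgery "28 – 42 after the last dose" (days, from the schedule): 64 + 28 = day 92 to 64 + 42 = day 106.
- CT day = surgery day + months × 30.44. Landmark = day 731.

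| CT | Day | Days left to day 731 | Share of 730 days |
|---|---|---|---|
| Month 3 | 183–197 | 534–548 | 73–75% |
| Month 6 | 275–289 | 442–456 | 61–62% |
| Month 12 | 457–471 | 260–274 | 36–38% |
| Month 18 | 640–654 | 77–91 | 11–12% |

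These figures describe scheduled contact, not bias. The protocol does not say how many patients would progress or how long they would live afterwards, so the bias cannot be computed.

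**5. Does survival contact to month 24 fit the planned study length?** Section 5.2.6 expects the study to end 2 years 4 months (28 months) after the last enrolment. Taking enrolment and first dose as the same day, month 24 after surgery falls at:

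- (63 + 28 + 730.5) / 30.44 = 27.0 months, to
- (63 + 42 + 730.5) / 30.44 = 27.4 months.

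The stated 28 months therefore accommodates the full post-operative calendar on nominal timing. With three cycle delays of 7 days, the latest surgery date and a 14-day late last visit, the figure is (63 + 21 + 42 + 730.5 + 14) / 30.44 = 28.6 months, slightly over.

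**The case against.** The strongest reply is that the intended rule can be recovered. The schedule marks survival status through month 24, and that row carries no progression stop. Note I to the schedule ends imaging after recurrence and refers to a follow-up period that goes on. The patient-withdrawal list in section IV, 1.3 does not name progression or new therapy. All of this stands as evidence of intent. It does not remove the conflict: the withdrawal list is expressly not exhaustive, and none of these passages says that survival contact continues after progression or qualifies the wording of 5.2.5.

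Three stronger readings are tempting and go too far.

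- *Deaths after progression will go unrecorded and OS is biased upward.* 5.2.5 ends scheduled visits. It does not forbid recording a known death, and 7.2 still applies to the same site. The bias requires both literal use of 5.2.5 and censoring at last contact, and censoring rules may be set in an SAP that is not shown.
- *5.2.5 contradicts the OS analysis in 5.4.3.2.* Kaplan-Meier accepts censored patients, so a visit stop can weaken that analysis without contradicting it. The textual conflict is with 7.2.
- *5.2.5 cuts off dosed patients who never have cystectomy.* Its visits are timed from surgery, so it says nothing about them. That is a separate gap, a silence rather than a contradiction.

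It is also fair to say that 7.2 is an end-of-trial provision, not a visit rule. But its condition of two years for all subjects can be met only if somebody collects the data.

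**Conclusion.** The conflict between 5.2.5 and 7.2 holds for operated patients who progress or start new anticancer therapy. Depending on which CT shows progression, 2 to 7 of the ten post-operative visits would be dropped, including one to three whose only purpose is survival status. If 5.2.5 is applied literally, OS is censored at last contact and the risk of death rises after progression, the 1- and 2-year OS rates would be too high by an amount the documents do not allow to be computed.

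The reach is limited. OS is a descriptive secondary endpoint in a single-arm study. pCR, the two-stage rule and the sample size are untouched. This is a wording conflict that should be reconciled because sites act on it, not evidence that survival data will be lost.

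**What to change.** Amend 5.2.5 to agree with 7.2. State that the progression/new-therapy stop applies to clinic assessments and imaging only, and that survival status continues on the existing post-operative calendar to month 24 regardless of progression or new therapy. A telephone contact is enough.

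The same sentence can cover dosed patients who never have cystectomy, since OS is also analysed in the safety set. Their calendar needs its own starting point, for example the drug safety visit, because the post-operative one is timed from surgery.

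Cost for operated patients: at most 7, 6, 4 or 2 telephone contacts for a patient whose progression is found at the month 3, 6, 12 or 18 CT, all at time points already listed. Consent must be checked to confirm that it covers contact after progression. No imaging or clinic visit is added, and on nominal timing the study need not run longer than 5.2.6 already expects.

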5.2.6 Study termination

Study termination was defined as the point in time when the final data from the clinical study was collected, that is, the point in time when the last study patient completed his/her last visit to the study center, and was expected to occur 2 years and 4 months after the last patient was enrolled in the study. The team leader unit has the right to terminate the study at any time. Reasons for early termination of the study may include, but are not limited to, 1) the incidence or severity of AEs in

this or other studies are suggestive of a health hazard to the patient; 2) The overall patient enrollment is unsatisfactory; 3) In the first stage (18 subjects), the effective cases with complete pathological response were less than 2.

If a decision is made to terminate the study, each investigator will be notified by the team leader unit. Patients who discontinue early should be viewed as soon as possible and scheduled for a drug safety/end-of-treatment visit, if necessary. The investigator may be notified to follow additional procedures to ensure that adequate consideration is given to the protection of the patient's interests. The investigator will be responsible for informing the Institutional Review Board (IRB)/Independent Ethics Committee of the premature termination of the study.

5.3 Study evaluation and procedures.

Patient safety and tolerability will be closely monitored throughout the study. All evaluations of each patient should be performed and documented in the medical records. Dosing will only occur after review of clinical assessments and local laboratory values, which must be obtained before each dose, and when dosing conditions are met as directed by the study protocol.

5.3.1 Screening

Screening phase assessments will be conducted within 28 days prior to enrollment and patients who agree to participate will sign up for an ICF prior to undergoing any screening procedures. The screening period starts on the first day of the screening procedure. Screening evaluations can be repeated as needed during screening; The investigator will evaluate a patient's eligibility for inclusion based on the latest screening assessments. Standard tests or test results performed ≤ 28 days before informed consent are available for screening assessments and do not require repeat testing unless otherwise specified.

Demographic data and medical history of 5.3.1.1

Demographic data will include date of birth (or age), gender, and race/ethnicity reported by self. Medical history including a variety of clinically significant medical, surgical or cancer history; • Fertility status; And history of drinking and smoking. Radiographic findings prior to enrollment were collected.

Fertility Women and Contraception in 5.3.1.2

Fertility is defined as the ability to conceive physiologically. .

Informed consent and screening records in 5.3.1.3

Written informed consent to voluntarily participate in the study must be obtained prior to performing any study-specific procedures. The ICFs of all enrolled and screened but not enrolled patients will be maintained at the study center. All screening assessments must be completed and reviewed before patients are admitted to the group, confirming that they meet all eligibility criteria.

5.3.2 Entry

5.3.2.1 Qualification Confirmation

The investigator will evaluate the eligibility of each patient for inclusion. Results of all screening procedures and associated medical history must be obtained before eligibility is established.

5.3.2.2 Patient ID

After obtaining informed consent, study center staff will assign a unique patient number to a potential study subject.

5.3.3 Safety assessment

5.3.3.1 vital signs

Vital signs included measurement of body temperature (C), pulse, and blood pressure (systolic and diastolic). Height (baseline only) and weight should be measured and recorded in the eCRF. Patients will be advised of the possibility of a delay in symptoms following infusion and to contact their study doctor if they develop this condition.

5.3.3.2 Physical Examination

During the screening visit, a physical examination will be performed that includes assessment of 1) head, eyes, ears, nose, and throat, 2) cardiovascular, 3) skin, 4) musculoskeletal, 5) respiratory, 6) gastrointestinal, 7) nervous system, and 8) urinary system. Any abnormalities identified during screening will be graded according to NCI-CT Cae Version 5.0 and documented in eCRF using the appropriate disease/condition term.

Limited symptom-specific physical examinations will be performed at follow-up visits (and as clinically indicated). Changes from baseline will be recorded. New or worsening clinically significant abnormalities should be recorded as AEs in eCRF.

5.3.3.3 Eastern Cooperative Oncology Group (ECOG) Physical Status: The ECOG physical status was evaluated during the study.

Laboratory safety inspection in 5.3.3.4

Serum biochemistry, hematology, coagulation, urinalysis, fecal analysis, infectious disease testing, pregnancy testing, thyroid function (required before enrollment), and blood type will be evaluated at the discretion of the investigator in the local laboratory, with certain required components to be collected.

The investigator used the results from the local laboratory for eligibility assessment, safety monitoring, and dosing decisions. Table 1

Table 1: laboratory test items

Serum biochemical test	hematology	blood coagulation	Urine analysis
------------------------	------------	-------------------	----------------

Alkaline phosphatase	red blood cell	Prothrombin time	pH
Alanine aminotransferase	count	Partial thromboplastin time	specific gravity
aspartate amino transferase	hemoglobin	or activated partial thromboplastin time	glucose
albumin	hematokrit	international normalized ratioinr	albumen
Bicarbonate or total carbon dioxide i	white cell count	Infectious disease examination	acetone/ketone body
Total bilirubin, direct bilirubin	platelet count	HIV antibody, hepatitis B	occult blood
Blood urea nitrogen or urea	Neutrophil count	two and a half	Fecal routine
Magnesium, chlorine, phosphorus, potassium, sodium, calcium	Eosinophil count	HCV antibody	Color, character
Creatinine, glucose	Basophil count	Thyroid function	Microscopic examination of leukocytes
Lactate dehydrogenase, total protein	Monocyte count	Free T3, free T4	Microscopic red blood cell
Creatine kinase (CK), CK-MBii	Lymphocyte count	Serum total thyroxine TT4	Occult blood test
		Serum total triiodothyronine TT3	
		Determination of thyroid stimulating hormone TSH	

Abbreviations: CK-MB, creatine kinase cardiac isoenzyme; I. If considered regional standard treatment, test for this. II. If CK-MB portion is not available, evaluate troponin I and/or troponin T instead.

5.3.3.5 electrocardiogram

For safety monitoring purposes, the investigator must review all 12-lead ECG records, and sign and date them. Paper or electronic copies of the ECG will be maintained at the study center as part of the patient's permanent study file.

5.3.3.6 echocardiography: echocardiography is optional.

5.3.3.7 pulmonary function: pulmonary function tests are optional and the tolerance to radical surgery is evaluated.

Adverse events in 5.3.3.8

Drug and radical surgical AEs will be graded and documented throughout the study according to the NCI-CTCAE, Version 5.0, and Clavien-Dindo scoring system. Toxicity will be characterized by severity, duration, and time to occurrence.

5.3.4 Tumor and Efficacy Evaluation

5.3.4.1 baseline neoplastic imaging will be performed prior to enrollment with multiparameter magnetic resonance imaging of the bladder (or pelvis) (which must be reassessed post-TURBT if TURBT) and computed tomography (CT) scans of the chest, whole abdomen, and pelvis (enhancement to be determined by the investigator if necessary).

While 5.3.4.2 is on treatment, multiparameter magnetic resonance imaging of the bladder (or pelvis) will be performed (with a conditional VI-RADS score) and computed tomography (CT) scans of the chest, whole abdomen, and pelvis (enhancement at the discretion of the investigator if

necessary) prior to and prior to the start of cycle 3 of neoadjuvant therapy according to RECIST version 1.1:

1. Assessed prior to the start of cycle 3 and continued treatment as planned if the patient did not develop PD; • if the patient has PD, subsequent treatment at the discretion of the investigator;

2. Pre-operative evaluation. If the patient meets the operation indication, the researcher shall select appropriate time to perform radical cystectomy according to the plan; If the patient is not suitable for surgery, the investigator decides to give subsequent treatment;

3. After radical surgery, the pathological stages after neoadjuvant treatment will be evaluated by the researchers based on the pathological results of surgical samples.

4. Computed tomography (CT) scans of the chest, whole abdomen, and pelvis are performed 3 months, 6 months, 12 months, 18 months, and 24 months after the radical resection (enhancement is judged by the researcher if necessary). The former shall prevail until the disease progression, death, withdrawal of informed consent, loss of follow-up, conclusion of study follow-up or initiation of new anti-cancer treatment (surgery) of the patient occur.

The investigator will evaluate the response using RECIST 1.1.

